9.15 Notification of Serious Adverse Events

Under IND regulations, 21 CFR Part 312.64, investigators are required to notify the

Sponsor promptly, within 24 hours of the sites' notification of any serious adverse events, deaths,

or life-threatening problems with the investigational drug. This regulation also requires that if the

adverse event is alarming, the investigator must notify the Sponsor immediately.

The Sponsor must be notified as detailed in section 9.16, "Reporting a Serious Adverse

Event." The Sponsor, in turn, will report all serious adverse events to regulatory agencies as

required. In addition to the serious adverse events described in section 9.7, other events that in the

investigator's opinion suggest a significant hazard, contraindication, or precaution should be

considered serious. This includes, but is not limited to, blood dyscrasias, endocrine disturbances,

hemorrhage from any site, or severe skin disorder. Additional examples are intensive treatment in

an emergency room or at home for allergic bronchospasm, blood dyscrasias or convulsions that do

not result in hospitalization, and development of drug dependency or drug abuse. Hospitalization

for elective surgery is not considered a serious adverse event. In addition, pregnancy is not a

Serious Adverse Event, but is reportable and must be reported per IND regulations and timelines,

21 CFR Part 312.64, on the SAE reporting form and submitted to the sponsor.

Patients who experience a serious adverse event must be given appropriate examinations

and treatment. The investigator must provide written information to the sponsor as soon as

possible.

When an investigator is in doubt when to report an event, the investigator should err on the

side of caution and contact the Sponsor.

9.17 Serious Adverse Experiences: After Study Participation

Preclinical data to date do not point to specific classes of adverse events for which patients may be at risk after completion of study participation. In order to monitor for unanticipated adverse events occurring after study participation, the following must be complied with:

- Any occurrence of a patient death is to be reported any time that the investigator becomes aware of the event
- A congenital anomaly in an offspring of a patient where that offspring has been born after the patient used study medications should be reported
- Any serious adverse event, for which, in the investigator's opinion, there is a reasonable possibility that the event could have been caused by the study drug, should be reported
- Any other serious adverse event should be reported if it occurred within thirty days following the last dose of study medication

9.18 Departure from Protocol for Emergency or Adverse Event

In medical emergencies, the investigator should use medical judgment and remove the patient from immediate hazard. As soon as possible after removing the patient from hazard, the investigator must contact Enterin Inc. by telephone to permit a decision as to whether the patient may continue in the study. The IRB should also be notified as to the type of emergency and the course of action. The case report form for the patient must describe the departure from the protocol and state the reason.

9.19 Data Safety and Monitoring Board

A Data Safety and Monitoring Committee (DSMB) has been established to monitor the safety of the subjects during the course of the study. The DSMB includes members with relevant clinical expertise, including a good understanding of the safety of medications for Parkinson's disease. These members include a statistician, a gastroenterologist and a neurologist. The methodology and the operating procedures for the safety reviews will be developed by the Chairperson in collaboration with the sponsor and will be documented in the DSMB Charter.

9.20 Review of Stage 1 Data by Data Safety Monitoring Board

When the last subject in Stage 1 has completed the course of dose escalation safety, PD and PK data will be reviewed by a DSMB, which will then provide a recommendation, based on guidelines established in the DSMB Charter, whether to advance to Stage 2. The starting dose for Stage 2 will be that dose which is safe and tolerable in all subjects and has a prokinetic effect in at least some ("STDE dose"). When the first ten subjects in Stage 2 have completed the course of dose escalation, data will be reviewed by the DSMB, which will then provide a recommendation, based on guidelines established by the DSMB Charter, whether to advance to the randomized controlled Period.

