therapeutic effect. Should there be more than 1 patient with AE grade 4 or 5 that is at least possibly

related to ENT-01 for doses less than 200 mg, the study will be put on an immediate safety hold

until an emergency DSMB meeting can be held to evaluate the study for possible discontinuation.

Dose-finding: Beyond the safety and tolerability, this Period will allow us to determine the dose

which is safe and tolerable in all 10 patients (STD) and which has a pro-kinetic effect in at least

some patients (STDE: Safe and Tolerable dose in all and pro-kinetic Effect in at least some). We

will start Period 3 with the STDE.

PERIOD 2.2 (Stage 1): Washout

Duration: 2 weeks

Patients will be observed off study drug and adverse events will be recorded. They will

continue to keep a daily diary throughout the period. They will continue to wear the I-Button for

five 24 hour periods between Days 1 and 5. During the second week, they will be restarted on all

original medications but will continue their diaries until the termination of the study. They will be

seen prior to study termination and BDI, MMSE, Trail making A and B, NMSQ, UM-PDHQ, PFS-

16, RBDQ, PDSS, PAQ-SYM and PAC-QOL will be administered.

Visit 2: Day 14

Patients will be reviewed prior to discharge and any adverse events noted.

DSMB review of Stage 1: The DSMB will determine whether to proceed to Stage 2.

PERIOD 3.1 (Stage 2a)

Run-in period for Cohort 2 (n=40)

Duration: 2 weeks

Conducted at home.

28

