• The patient will self-administer the Sitzmarks capsule (contains 24 radiopaque markers; Konsyl Pharmaceuticals, Texas, USA) by mouth with water on Days 8,9, and 10 and will consume their usual diet during this period. The patient will abstain from using suppositories or enemas until they return on Day 11. An abdominal XR will be scheduled on Day 11

Day 11 – Site Visit 2

An abdominal XR will be obtained to determine the location and the extent of elimination

of the radiopaque markers. Patients who expel at least 80% (19 or more of the markers) have

grossly normal colonic transit. If remaining markers are scattered about the colon, the condition is

most likely hypomotility or colonic inertia. If remaining markers are accumulated in the rectum or

rectosigmoid, the condition is most likely functional outlet delay. Radiographs will be collected in

electronic format and subsequently analyzed in blinded manner by a centralized reader ([name] MD, and [name], MHA, Division of Gastroenterology and Hepatology, Mayo

Clinic). The patient will be given study medication (B) and a PAC-SYM and PAC-QOL to take

home. This will trigger randomization to treatment or placebo and to PK or no PK.

Day 14- Phone call

Patients will be asked to complete the PAC+SYM and PAC-QOL questionnaires. They

will be instructed to take the medication the following morning on an empty stomach and not to

eat anything for at least 60 minutes thereafter. Baseline complete, spontaneous bowel movements

(CSBM) will be calculated from the diaries at the 14 day phone call as CSBM/entries x

7.Baseline PAC-SYM and PAC-OOL and baseline ease of passage and consistency will also be

obtained at this time-point.

PERIOD 3.2 (Stage 2): Multiple doses

Safety, tolerability and pro-kinetic effect of orally administered multiple-dose ENT-01 in

Sentinel Group followed by Remaining Cohort

Cohort 2 (40 patients, of which 10 comprise the sentinel group):

Duration: 17-19 days

The purpose of this period is to demonstrate the continued pro-kinetic effect beyond that

of a single-dose, to confirm the effective pro-kinetic dose for each individual and to establish the

safety, tolerability and PK of multiple doses of ENT-01. A pro-kinetic dose is defined as the dose

that results in a spontaneous, complete stool on at least two of the three dosing days. Once the

pro-kinetic dose is established, and assuming there are no safety concerns, each patient will be

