
be calculated as CSBM/#fixed dose days x 7. The primary end-point is obtained by comparing this number to the baseline CSBM obtained at the end of the run-in period.

2: SUPPOSITORY/ENEMA RESCUE USE DURING DOSE ESCALATION IN STAGE

Patients will wear I-Buttons starting with the lowest dose (e.g. 75 mg) and will remove them on day 5 of the wash-out period. The remaining 30 patients will start on STDE (e.g. 75mg) as soon as they have completed the Run-in Period and will follow the same incremental dosing regimen until they reach their LSTDEi or maximum tolerated dose. These regimens and adjustments are shown in the schematic below.

Once the LSTDEi has been established, each patient will remain on that dose for two to four additional days prior to randomization in Period 4 (5 to 7 consecutive days on prokinetic dose)

N.B. Primary end-point is obtained by comparing stool diary at this point with baseline diary on rescue medication at the end of the run-in period.

Visit 3 for non-PK patients (Day before Randomization).

Non- PK patients will come to the site for a visit to return any unused study drug (B), receive 6 daily doses of randomized drug (A or C), Sitzmarks capsules and will complete all the questionnaires listed below. They will be sent home with 6 daily doses of A or C and Sitzmarks capsules and will return for Visit 4 on Day 6 of randomization to complete all the questionnaires.

Go/No-go decisions:

Safety: We are assuming that no more than 1 patients out of forty (2.5%) will have an adverse event of grade 4 or 5 that is at least possibly related to ENT-01 in this Stage. Should there be more than 1 patient with an AE grade 4 or 5 that is at least possibly related to Enterin-0 in this cohort

of 40 patients, the study will be put on an immediate safety hold until an emergency DSMB meeting can be held to evaluate the study for possible discontinuation.

Tolerability: We are assuming that all patients will exhibit a pro-kinetic effect at a dose lower than DLT and less than or equal to 175mg. Patients reaching DLT before a pro-kinetic effect will be terminated if the highest dose for the patient without a DLT was the STDE dose. Otherwise the patient will be treated at the highest dose at which they did not experience a DLT if they are randomized to the treatment arm (or will receive the equivalent dose of placebo).

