Efficacy: We are assuming that a consistent pro-kinetic effect will be observed in all patients. Patients in whom a pro-kinetic effect is not observed at the maximum dose of 175mg will continue to take 175mg for another 2 days and enter the randomized period. If they are randomized to treatment, they will be given 175mg/day for the 6 randomized dosing days.

Individual stopping criteria:

Patients who reach DLT before a pro-kinetic effect, exhibit LFT elevation above 3xULN, have a 10% or greater reduction in body weight or those with a non-DLT gastrointestinal AE > grade 3 within 24 hours of taking ENT-01 that is at least possibly attributable to ENT-01 will be terminated.

Pharmacodynamics: Patient will record bowel movements, ease of passage, consistency and suppository usage in the daily diary throughout the Period and transmit the information to the coordinator every evening.

Sleep assessment: Patients will wear the I-Button throughout the dosing period and remove it only during bathing periods.

STDE DOSE in this example is 75 mg, that being the lowest dose that is safe and tolerable in all subjects and has a prokinetic effect in at least some LSTDEi is the lowest safe and tolerable dose that produces a prokinetic response reached by an individual in at least 2 of 3 days at that dose Subject Day1 Day2 Day3 Day4 Day5 Day6 Day7 Day8 Day9 Day9 Day1 Day12 Day12 Day13 Day14 Day15 Day16 Day17 Day18 Day19 Day20 Day21 Day22 100mg 100mg 100mg 100mg 100mg 100mg 100mg ng 100mg 100mg 100mg 100mg 100mg 100mg 100mg 100mg 125mg 125mg 125mg 125mg 125mg 125m 150mg 150mg 150mg 150mg 150mg 150mg 150mg COHORT 1, 100mg 100mg 100mg 100mg 100mg 100mg Stage 2. SENTINEL PERIOD 3.2, g 125mg ng 150mg 150mg 150mg 150mg 150mg 150mg ROUP N=10 (COHORT 1) 75mg | 75mg | 75mg Safety and tolerability of 3 day dosing. and extension to a total of 5 COHORT 2 doses GROUP, N=32 **RUN-IN PERIOD FOR SUBJECTS 11-40** Day 23 Day24 Day25 Day26 Day27 Day28 Day29 Day30 Day31 Day32 Day 33 Day34 Day35 Day36 Day37 Day38 Day39 Day40 Day41 Day42 Day43 Day44 COHORT 2 GROUP, N=32 11-40

Schematic of Stage 2, Period 3.2 with hypothetical dosing regimen

DSMB: The DSMB will meet at the end of the fixed dose period for the ten sentinel patients.

LSTDEI LSTDEI LSTDEI LSTDEI

PERIOD 4

(Stage 2): Randomized, double-blinded treatment period to determine the effect of orally administered ENT-01 on pharmacodynamics and motility.

Duration: 6 days

Visit 3 for PK patients (Day 1 of randomization):

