PK subjects will come to the site on Day 1 of randomization ON AN EMPTY STOMACH and return their unused study drug at that time point. They will receive the first dose of medication at the site following the first PK blood draw, and complete the questionnaires listed below. PKs will also be performed at 1, 2, 4, and 8 hours post-dose. A sample for liver function tests will be drawn with the 8-hour post-dose PK draw. They will receive 4 daily doses to take home, then return on Day 6 to receive their 6th dose at the site after their first PK draw of the day. PKs will again be obtained post-dose at 1, 2, 4 and 8 hours, a sample for liver function tests will be drawn with the 8-hour post-dose PK draw, and all the questionnaires completed.

Following the 5-7 day course on the pro-kinetic dose, ALL patients will be randomized to drug or placebo and enter Period 4. Randomization will be 1:1 to treatment vs. placebo. Randomization will occur in accordance with the randomization schedule generated by [name] at Weill-Cornell Medical College. Patients and study staff will be blinded to actual study treatment and will remain blinded throughout the remainder of the study. BDI, MMSE, Trail making A and B, NMSQ, UM-PDHQ, PFS-16, RBDQ, PDSS, PAC-SYM and PAC-QOL will be administered prior to randomization. The UPDRS will be administered and weight and vital signs will be taken).

Assuming randomization is to treatment group, the patient will remain on that dose daily for a 6 day period (6 dosing days). Patients randomized to placebo will be switched to the same number of placebo tablets as they were taking prior to switching. All patients will continue to keep daily diaries during this period. The use of rescue medication (suppositories and enemas) for constipation will be permitted as needed if a bowel movement has not occurred for 3 days and recorded in the diary. Patients will be contacted daily. The suppository will be taken on the evening of the third day as shown in Figure 1 above. *Any bowel movement produced as a result of rescue medication will not be counted.*

Patients reaching their tolerability limit at a dose lower than a clinically effective dose (STDE) will be terminated from the study. We have included 40 patients in this Stage to allow for 15% drop-outs for reasons including tolerability.

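### The DSMB review of the ten Stage 2 sentinels gates the randomized period in Protocol 9.20, but the patient flow in Protocol 3.1 does not wait for it, and nothing ties first dosing of patients 11-40 to sentinel data

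*Protocol*

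**What the plan says.** Protocol 9.20 sets the trigger: "When the first ten subjects in Stage 2 have completed the course of dose escalation, data will be reviewed by the DSMB". The board then recommends "whether to advance to the randomized controlled Period". That is a gate in front of Period 4.

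Protocol 3.1, at the end of Period 3.2, gives another time: "The DSMB will meet at the end of the fixed dose period for the ten sentinel patients". No decision is attached there. For Stage 1 the same section does state one: "DSMB review of Stage 1: The DSMB will determine whether to proceed to Stage 2".

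Entry to Period 4 is described patient by patient: "Following the 5-7 day course on the pro-kinetic dose, ALL patients will be randomized to drug or placebo and enter Period 4". The only check that section 3.1 names just before this step is the sponsor medical officer's review of stool diaries for adequate dosing.

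For the rest of the cohort, Protocol 3.1 says: "The remaining 30 patients will start on STDE (e.g. 75mg) as soon as they have completed the Run-in Period". The title of Period 3.2 ("Sentinel Group followed by Remaining Cohort"), the overview table in Protocol 3 and SAP 2.1 all put the sentinels first. The hypothetical Period 3.2 schematic carries the label "RUN-IN PERIOD FOR SUBJECTS 11-40" while the sentinels are being dosed, and appears to start those patients on Day 23.

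**The concern.** A sentinel group protects later patients only if its data are looked at before they are dosed. Protocol 1.3 describes this as the first oral dosing of ENT-01 in man. Stage 1 gives single doses only, so the Stage 2 sentinels supply the first repeated-dose oral data. The dog-based margin in Protocol 1.3 falls from about 70-fold at the highest single dose to at least 9-fold at the highest repeated dose.

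A sentinel who responds early cannot satisfy both rules. Section 9.20 would have that patient wait for the review of all ten; section 3.1 sends the patient on after 2-4 fixed-dose days. For patients 11-40 the issue is an omission: their start depends only on their own run-in, so the intended order rests on scheduling and not on any condition about sentinel data.

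**Working it through.** **Inputs.** Three dosing days per level and 2-4 fixed-dose days (Protocol 3.1, Period 3.2). Period 4 lasts 6 days (Protocol 3.1). The dosing maximum in Stage 2 is 25 days (Protocol 11). Levels are 75, 100, 125, 150 and 175 mg: 75 mg is the protocol's example starting dose, and SAP 2.1 gives 75-175 mg as the range under the July 2017 version. A common start day for all sentinels is my assumption.

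**The plan's own figures.** 5 levels × 3 days = 15 days of escalation. Adding 2-4 fixed days gives 17-19 days, the stated length of Period 3.2. Adding 6 days gives 23-25, which agrees with the 25-day maximum.

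**Calendar.** For level k (1 to 5) and f fixed days (2 to 4): escalation ends on Day 3k, fixed dose on Day 3k + f, Period 4 starts on Day 3k + f + 1 and ends on Day 3k + f + 6.

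| Dose | Escalation ends | Fixed dose ends | Period 4 starts | Period 4 ends |
|---|---|---|---|---|
| 75 mg | 3 | 5-7 | 6-8 | 11-13 |
| 100 mg | 6 | 8-10 | 9-11 | 14-16 |
| 125 mg | 9 | 11-13 | 12-14 | 17-19 |
| 150 mg | 12 | 14-16 | 15-17 | 20-22 |
| 175 mg | 15 | 17-19 | 18-20 | 23-25 |

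**Against the 9.20 point** (slowest sentinel ends escalation), where the slowest is m levels above the early responder:
- m = 1: entry on Day 3k+3 to 3k+5 against Day 3k+3. Same day or 1-2 days after, never before.
- m = 2: the same entry days against Day 3k+6. Always 1-3 days before.
- m = 4 (75 against 175 mg): Period 4 ends on Day 11-13 against Day 15. Always finished first.

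**Against the 3.1 point** (slowest sentinel ends fixed dose, with f′ fixed days):
- m = 1: entry comes first when f + 1 < 3 + f′, that is f < f′ + 2. The protocol ties 3 or 4 fixed days to a Saturday or Sunday, and a sentinel one level slower runs three weekdays later. Over the seven weekdays the pairs (f, f′) are (2,2) three times, then (3,2), (4,2), (2,3) and (2,4). Entry comes first in 6 of 7; (4,2) is a tie.
- m = 3: Period 4 has ended first when f + 6 < 9 + f′, that is f < f′ + 3. The extreme case is 4 < 5, so this always holds.
- m = 4: Day 11-13 against Day 17-19.

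**Could early responders wait on drug?** A 175 mg sentinel with 4 fixed days uses 15 + 4 + 6 = 25 days, which leaves none for a review held after fixed dosing. If the board met on Days 20-22 and the sentinels stayed on drug until then, 6 further active days would give 26-28 and exceed the maximum. A 75 mg responder held to Day 15-19 would also have 15 − 3 = 12 to 19 − 3 = 16 fixed-dose days, instead of 2-4, in the denominator of the primary endpoint.

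**The case against.** The strongest reply is that the gate exists. Section 9.20 is operative text, Protocol 12.10 requires the instructions to be followed exactly, and the meeting in section 3.1 is the last item before Period 4. A site that reads both sections would hold. That stands against a claim that the randomized period has no DSMB gate, which a reader of section 3.1 alone might infer. It does not remove the conflict, because section 3.1 gives each patient an entry time that can fall before the review of all ten.

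The two review times may also be loose wording for one meeting. A board that meets at the end of fixed dosing has seen completed escalation, as 9.20 requires, and the literal gap is only 2-4 days per patient. This stands: the difference in dates alone would be minor.

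A reader might go further and say that the protocol contradicts itself on patients 11-40. The documents do not support that. Section 9.20 does not make their first dose depend on the DSMB either, and the stated order, with the schematic's apparent Day 23 start, suggests that they were meant to follow. Tying their start to the review is a safety improvement, not the repair of a contradiction.

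Finally, the DSMB Charter, which holds the review guidelines and stopping rules, is not available and may state a hold.

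**Conclusion.** The point holds, with modest consequences. Under the July 2017 protocol an early-responding sentinel can enter Period 4 before the review that 9.20 places ahead of it. At 75 against 175 mg that patient has finished Period 4 before either review point. Patients 11-40 have no written condition on sentinel data before their first dose. The day counts rest on a common start at 75 mg; a staggered start would change them.

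A serious safety gap should not be inferred. Period 4 gives the same dose or placebo for 6 days, so entering it adds no escalation. The Stage 1 DSMB decision, the hold for more than one related grade 4-5 event, the individual stopping criteria, daily contact and the board's power to recommend a stop all remain.

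The SAP reports that the 02 February 2018 amendment removed the randomized period, so the Period 4 part concerns only patients treated under the July 2017 version. SAP 2.1 lists only that removal and a new 100-250 mg range as changes, which suggests that the wording on patients 11-40 survived. The amended protocol is not available to confirm it. No sample-size or power figure depends on this point.

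**What to change.** 1. Use one review point in Protocol 3.1 and 9.20: all ten sentinels have ended the fixed-dose period. Attach the go/no-go recommendation to it in section 3.1, as is already done for Stage 1.
2. State in section 3.1 that patients 11-40 receive no study drug until that recommendation is given, and time their 14-day run-in to end afterwards. With 175 mg as the top dose, a run-in starting on sentinel Day 9 gives a first dose on Day 23 and leaves Days 20-22 for the meeting. Write the rule as a condition and not as a day number: under the amended range, seven levels × 3 days is already 21 days of escalation.
3. State in 9.20 that sentinels proceed individually to Period 4 under the existing individual stopping rules. Nobody is then held on open-label drug beyond the 2-4 fixed days or the 25-day maximum, and the primary endpoint's denominator is unchanged.

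The cost is wording in two sections and a somewhat later start for some of patients 11-40. The third change gives up the cohort-level gate for the sentinels themselves. That is acceptable because Period 4 does not raise their dose.
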